Comparison (a) REDvent-acute versus control: A 1-day reduction in length of weaning is considered clinically significant (less sedative exposure, fewer nosocomial infections, lower healthcare costs). With a sample size of 276 patients (138 per arm), up to 12% mortality and 1% attrition or incorrect randomization, a minimum of 240 patients (120 per arm) will be available for analysis of the acute phase. Power is based on 2 planned methods for analysis: cox proportional hazard ratios for multivariable analysis and univariate analysis with an independent t-test using log transformation (as needed) to account for the expected distribution of weaning duration. For univariate analysis using the assumptions above, we would be able to detect a ≥ 1 -day reduction in weaning duration with an alpha of 0.05 and power of 0.9 (Figure 7). For the cox proportional hazard model, we would be able to detect a relative hazard ratio of 1.5 (ratio between control/intervention group) with a power of 0.9 or a hazard ratio of 1.4 with a power of 0.8.

Comparison (b) REDvent-weaning versus control: Patients who fail the initial SBT will undergo the weaning phase randomization. From our pilot data, approximately 25% of patients exposed to the intervention passed the initial SBT, corroborating previous studies.¹⁵ Thus, at least 180 patients (90 per arm) will receive weaning phase interventions. Using the same assumptions as above, we will be able to detect a ≥ 1 day

reduction in the length of the weaning phase (Figure 8), or a hazard ratio of 1.5 with an alpha of 0.05 and power of 0.8. Patients who do not pass the SBT by 28 days post the weaning phase randomization will be censored for analysis, as study interventions and daily monitoring will end on day 29.

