Secondary Outcomes for SA 1: The 28 and 60 Day Ventilator Free Days (28D VFD, 60D VFD) will be secondary outcomes of this aim. Groups for VFD analysis will be based on any exposure to the intervention (acute or weaning) because some patients will never undergo a weaning phase randomization (i.e. died or were extubated right after the acute phase). If patients who died as well as those who dropped out are included in the VFD analysis, with the assumptions above regarding expected passing rate of SBTs, the estimated distribution of patients in 3 distinct groups will be: (a) REDvent only (n=108); (b) REDvent and control (n=90); (c) control only (n=102). We anticipate children in the REDvent only arm will have the most 28 D VFDs (anticipation 22), and those in the control only arm the least (anticipation 20). Directly comparing control only patients to REDvent only patients, with an expected standard deviation for VFDs between 5 to 9 days, we will be able to detect a 2-day change in VFDs between groups with a power between 0.35 and 0.82. Re-intubation rates are expected to be 10%, allowing us to confirm that REDvent is not inferior to usual care in regards to re-intubation with a non-inferiority margin of 0.10 with a power of 0.8 and alpha of 0.05. Finally, to ensure that REDvent is promoting greater patient effort of breathing and that the intervention does not alter clinical practice in the usual care arm, we will compare time weighted average values for direct measures of patient effort of breathing (PRP, PTP, Diaphragm Contractile Activity), and ventilator settings between intervention and control groups, and monitor the separation between groups over the time of the study.

D.6.4.2 SA2 Analysis Plan: To determine if changes to direct measures of respiratory muscle strength, load, effort, and architecture throughout the duration of MV are related to weaning outcomes.

Analysis and Sample Size: The primary outcome of this aim is weaning duration (as defined above). For this analysis, we will compare how each respiratory measure detailed in the data collection table relates to weaning duration. For respiratory muscle

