After the first 75 patients were enrolled in the study a new milestone accrual plan was created to account for the increase in the percentage of patients meeting the primary outcome. Previously, it was assumed 20% of patients would not meet the outcome, however, data after 75 patients revealed this was 13% and the total sample size requirement was adjusted down from 300 to 276 patients. The number of patients targeted per group to meet the primary outcome was unchanged, at 120 per group. This updated milestone accrual plan was reviewed and accepted by the NLHBI and DSMB.

January 2023 - Change in primary analysis for length of weaning

Blinded, non-inferential summary statistics and distributions were assessed for the length of weaning outcome by the primary statistician as part of the data cleaning process. It was revealed that length of weaning might not be optimally analyzed as a continuous variable because SBTs were conducted once a day, with most patients passing their SBT within the first three days. In addition, enrollment had been affected by the COVID-19 pandemic and a new milestone accrual plan was requested by the NHLBI. As the observed distribution appeared more count-like, the primary analysis model was changed to Poisson or Negative binomial regression to better fit the data and satisfy assumptions. This decision was made by the senior biostatistician who was blinded to the randomization groups.

The sample size was re-estimated based on a minimum detectable difference for a reduction in the number of weaning days in the REDvent-acute vs. usual care-acute group using negative binomial regression. This yielded a minimal sample size of 230 patients to detect a reduction of 0.36 to 0.75 days when usual care had an average number of weaning days between 1 and 4, respectively with a power of 80%. This estimate of 230 patients accounted for the 13% loss in those meeting the primary outcome. This updated sample size estimate was reviewed and accepted by the NHLBI and DSMB. Based on this, the milestone accrual plan was revised, and enrollment was planned to continue through March 2024 with a target sample size between 230-276.

May 2024 – Change in primary analysis for length of weaning and PiMax

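### The amended protocol enrols 276, but its ventilator-free-day groups still sum to 300; the stated VFD power of 0.35–0.82 should read about 0.33–0.77

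*Combined protocol and SAP*

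**What the plan says.** In the amended protocol, D.6.4.1, Comparison (a) gives the enrolment and expected losses: "With a sample size of 276 patients (138 per arm), up to 12% mortality and 1% attrition", leaving 240 evaluable. Comparison (c) splits those 240 into 78 REDvent only, 72 control only and 90 mixed.

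The paragraph headed Secondary Outcomes for SA 1, in the same section, sets out the VFD groups. Its condition is "If patients who died as well as those who dropped out are included in the VFD analysis", and the sizes are "a) REDvent only (n=108); (b) REDvent and control (n=90); (c) control only (n=102". It anticipates 22 VFDs for REDvent only and 20 for control only. The power statement reads: "Directly comparing control only patients to REDvent only patients, with an expected standard deviation for VFDs between 5 to 9 days", the trial can "detect a 2-day change in VFDs between groups with a power between 0.35 and 0.82". The A2 Protocol Summary repeats this range under Aim 1.

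D10 of the amended protocol explains that the target fell from 300 to 276 because expected losses fell from 20% to 13%, with the 240 evaluable patients unchanged. The January 2023 entry of the final SAP (July 2024) lowers the minimum again to 230, "with a target sample size between 230-276". No other power for VFDs is given.

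**The concern.** The VFD groups count every enrolled child, so they must sum to the enrolment. They sum to 108 + 90 + 102 = 300, while the same section enrols 276. The sizes and the power range are those of the 300-patient protocol. The mortality, attrition and enrolment figures around them were updated, but this paragraph was not.

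VFDs are the first secondary endpoint listed and the outcome named for the Phase III trial that is meant to follow. Anyone weighing a null or borderline VFD result would rely on this power statement, and it describes a larger trial than the amended one.

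**Working it through.** **Inputs.** Group sizes, the 2-day difference and the SD of 5 to 9 days come from D.6.4.1, Secondary Outcomes for SA 1. The evaluable split of 78/90/72 (REDvent only, mixed, control only) comes from Comparison (c). Enrolment and losses come from Comparison (a) in each version of the protocol. The minimum of 230, which includes the 13% loss, comes from the January 2023 entry of the final SAP. Alpha is not restated for VFDs; 0.05 two-sided is assumed, as in the SAP's primary power statement.

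**Step 1: how 108/90/102 arises.** At 300 enrolled, 13% + 7% = 20% are non-evaluable, which is 60 patients. Assume they divide equally between the acute arms, 30 each. Then REDvent only is 78 + 30 = 108, control only is 72 + 30 = 102, and mixed stays at 90. This rebuilds the plan's three sizes exactly.

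**Step 2: the same construction at 276.** Non-evaluable patients are 276 − 240 = 36, or 18 per acute arm. REDvent only is 78 + 18 = 96, control only is 72 + 18 = 90, mixed is 90, and the sum is 276.

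**Step 3: at the 230 minimum.** Evaluable patients are 230 × 0.87 ≈ 200, leaving 30 non-evaluable, or 15 per arm. Scaling the split by 200/240 gives 65/75/60, so the groups are 65 + 15 = 80, 75, and 60 + 15 = 75.

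**Step 4: power.** Two-sample t-test with noncentrality λ = 2 / (SD × √(1/n₁ + 1/n₂)) and n₁ + n₂ − 2 degrees of freedom. For example, at 108/102 and SD 5, √(1/108 + 1/102) = 0.1381, so λ = 2 / (5 × 0.1381) = 2.90.

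| Enrolled | REDvent only / control only | λ, SD 9 | Power, SD 9 | λ, SD 5 | Power, SD 5 |
|---|---|---|---|---|---|
| 300 | 108 / 102 | 1.61 | 0.360 | 2.90 | 0.822 |
| 276 | 96 / 90 | 1.51 | 0.325 | 2.73 | 0.774 |
| 230 | 80 / 75 | 1.38 | 0.279 | 2.49 | 0.696 |

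The first row reproduces the stated 0.35–0.82 to within about one point. A one-sided test at 108/102 gives 0.486–0.895 and does not fit. The evaluable-only groups (78/72: 0.272–0.681) and the full acute arms of 150 (0.483–0.932) do not fit either. The stated range therefore belongs to the 300-patient groups.

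**Sensitivity.** Scaling 108 and 102 by 276/300 = 0.92 instead gives 99.4 and 93.8, with power 0.336 to 0.789. The upper end falls on either method. The lower end barely moves on this one.

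**The case against.** The best case for leaving the text alone is that little turns on it. At 276 the power falls by about 5 points at SD 5 and by 2 to 3 points at SD 9. The plan already admits power as low as 0.35, claims more than 0.8 only for weaning duration, and leaves adequate VFD power to a Phase III trial. Nothing was sized on VFDs. All of this stands and keeps the point small, but it does not make 300 the right total or 0.35–0.82 the right range.

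A second objection also stands. The final SAP changes the VFD analysis from competing-risks regression to a negative binomial model (Table 1, January 2023) and makes the four-group comparisons exploratory and conditional. A corrected t-test power is therefore a correct figure for a method no longer planned, and the correction should say so.

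Two stronger readings are tempting, but the documents do not support them.

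- A reader might infer that the trial delivers only 0.28–0.70. But 230 is the floor of a 230–276 target, so that range is a lower bound and not the design.
- A reader might infer that the randomised acute arms offer better power for the same 2 days: 138 against 138 gives 0.45–0.91. But the 2-day difference is anticipated only for REDvent only against control only. The acute arms also hold mixed patients: 120 − 78 = 42 in REDvent-acute and 120 − 72 = 48 in control-acute. The documents give no mean for mixed patients. If it is 21 days, the arm means are (96 × 22 + 42 × 21)/138 = 21.70 and (90 × 20 + 48 × 21)/138 = 20.35. The difference is about 1.35 days (1.33 to 1.37 for mixed means of 21.5 to 20.5), and the power is about 0.24–0.61.

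**Conclusion.** The point holds. The group sizes and the power range in the VFD paragraph are carried over from the 300-patient protocol and do not describe the amended trial. At 276 the groups are 96/90/90, and the power for a 2-day difference is about 0.33 (SD 9) to 0.77 (SD 5), against the stated 0.35 to 0.82.

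This rests on three assumptions: two-sided alpha of 0.05 for VFDs, a t-test, and non-evaluable patients divided equally between the acute arms. The last is not written in the plan, but it rebuilds 108/90/102 exactly at 300. The lower bound of about 0.28–0.70 further assumes that 230 means enrolled patients and that the 78/90/72 split scales down unchanged.

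A reader might also infer that the primary analysis has lost power through this error. It has not: the 240 evaluable patients behind the primary power did not change between 300 and 276, and the 78/72/90 split built on them still stands.

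**What to change.** In D.6.4.1 of the amended protocol, Secondary Outcomes for SA 1, restate the groups as 96/90/90 and say that non-evaluable patients are assumed to divide equally between the acute arms. There and under Aim 1 in A2, restate the power as about 0.33–0.77, with about 0.28–0.70 as the lower bound if enrolment stops at 230. Add one sentence saying that this is a t-test figure for REDvent only against control only, whereas the final SAP models VFDs by negative binomial regression and treats the four-group comparisons as exploratory. Do not substitute a 138-against-138 figure that keeps the 2-day difference.

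The cost is a few sentences and a slightly less favourable stated power. Trial conduct, the primary analysis and the enrolment target do not change.

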Aim 1: The primary outcome is weaning duration. Sample size has been determined to adequately power 3 separate comparative analyses: (a) REDvent-acute versus Acute Phase control (b) REDvent-weaning phase versus Weaning Phase control (c) REDvent both phases versus control both phases. Power is based on 2 planned methods for analysis: cox proportional hazard ratios for multivariable analysis and univariate analysis with an independent t-test using log transformation (as needed) to account for the expected distribution of weaning duration. For all three of the planned comparisons above, with the proposed sample size we would be adequately powered (>0.8) to detect a difference in weaning duration of ≥ 1 day, or a hazard ratio of ≥ 1.4 between groups. The secondary outcomes are ventilator free days and extubation failure. Directly comparing control only patients to REDvent only patients, with an expected standard deviation for VFDs between 5 to 9 days, we will be able to detect a 2-day change in VFDs between groups with a power between 0.35 and 0.82. Re-intubation rates are expected to be 10%, allowing us to confirm that REDvent is not inferior to usual care in regards to re-intubation with a non-inferiority margin of 0.10 with a power of 0.8 and alpha of 0.05.

Aim 2: The primary outcome of this aim is weaning duration. For respiratory muscle strength we will compare the first measured aPiMax (after resolution of the acute phase, before the first SBT), the trajectory and value of the daily aPiMax during the weaning phase prior to extubation, the lowest and highest measured aPiMax, and aPiMax on the day of extubation against weaning duration. For analysis, aPiMax will be dichotomized at 30 cmH₂O, and weaning duration will be compared between patients with aPiMax > 30 versus ≤ 30 cmH₂O using a t-test with or without log-transformation, or Mann-Whitney U test, depending on the distribution. From our preliminary data, we anticipate at least 35% of patients (n=84) will have aPiMax ≤ 30 cmH₂O. Based on a similar power analysis as presented above, this would allow us to determine whether low aPiMax

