Monitoring: The study will one planned interim analysis at 138 patients, with no rules planned for early stopping, given the low risk nature of this study and the high degree of physiologic data collected. In addition, there will be an early safety check after approximately 50 patients are enrolled, to review rates of adverse events between groups. There will be review of adverse events by the DSMB during scheduled meetings twice a year, or as requested.

A3 Primary Hypothesis and Specific Aims

Our central hypothesis is that REDvent use will reduce ventilator-induced respiratory muscle weakness, leading to shorter time on MV by enhancing the patient's capacity for effective, unsupported ventilation and by facilitating MV weaning. This will be specifically tested with 3 complementary specific aims:

SA1: To determine if REDvent acute and/or weaning phase protocols can shorten the duration of weaning from MV (Primary outcome). We expect that patients randomized to receive REDvent-acute will either pass their first SBT or experience a shorter duration of weaning when compared to usual care. In addition, patients randomized to receive REDvent-weaning will experience a shorter duration of weaning compared to usual care. Secondary outcomes include 28-day Ventilator Free Days and extubation failure.

SA2: To determine if changes to direct measures of respiratory muscle strength, load, effort, and architecture throughout the duration of MV are related to weaning outcomes. We expect that diminished respiratory muscle strength (low PiMax), and diaphragm atrophy (ultrasound) will be prevalent after resolution of the acute phase of MV, and the combination of high respiratory load (or effort) with low PiMax will be a major factor leading to prolonged weaning and weaning failure (failure of SBT).

SA3: To determine if patient effort of breathing during both acute and weaning phases of MV is independently associated with the development of respiratory muscle weakness. We expect that after controlling for confounding variables like age, diagnosis, sedation, use of neuromuscular blockade, and other risk factors for neuromuscular weakness, children who maintain normal effort of breathing in the acute or weaning phases will have higher respiratory muscle capacity as measured by PiMax.

B Background

B1 Prior Literature and Studies

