D.3.4 Acute Phase Monitoring, both arms: Patients will be fitted with an esophageal manometry catheter, will undergo diaphragm ultrasound measurements, and will be connected to RIP bands during SBTs. Volumetric capnography with an airway flow sensor will be placed at the end of the endotracheal tube to measure Carbon dioxide concentration, tidal volume, and airway pressures.

Once the patient passes the oxygenation test, an airway occlusion maneuver will be performed to measure neuromuscular strength, followed by a SBT. Daily SBTs are required and will be performed between 9 and 11 AM on CPAP of 5 cmH₂O. The primary study outcome (length of the weaning phase) is defined as the time from initiation of the first SBT until successful passing of an SBT (or extubation, whichever comes first). We will use validated objective criteria to define successful passing of the SBT, and track delays in extubation (> 6 hr between SBT passing and extubation). These criteria are based on our previous publications and are detailed in the description of the primary outcome above, and again below.^{16, 75} Patients who fail the initial SBT will move on to the weaning phase, and will undergo the weaning phase randomization to allocate treatment or control arms for weaning management.

D.3.5 Spontaneous Breathing Trials and success/failure

Variable	Failure within 2 hours
pH (arterial or capillary)	< 7.32
End tidal CO ₂	↑10 mmHg from baseline
Oxygenation	FiO ₂ > 0.5 and SpO ₂ < 90% on PEEP = 5 cmH ₂ O
HR	↑ > 40 BPM over baseline
Rapid Shallow Breathing Pattern (RSBI) (bpm/ml/kg)	≥ 12

Pressure.Rate.Product (PRP)	>500
Retractions	Moderate or Severe Retractions

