For the outcome of SBT passage, if any of the above criteria are met during the 2 hour SBT, the patient will be labeled as failing the SBT for study purposes. Once any of these failure criteria are met, the respiratory therapist will alert the clinical team. The clinical team may choose to stop the SBT, in which case the patient will be returned to the previous ventilator settings, and weaning phase randomization will occur. If the patient is randomized to REDvent-weaning, they will be placed in PS/CPAP mode and pressure support will be titrated to achieve PRP between 200-400 (to max of 20). PEEP may be adjusted between 5 and 10 cmH₂O. The clinical team may alternatively choose to continue the SBT or to extubate the patient. If the patient is extubated, post-extubation management (and subsequent re-intubation management) will be usual care. If the patient is not extubated but the SBT is terminated by the clinical team, then weaning phase randomization will occur at that point.

Monitoring during the SBT will include placement of Respiratory Inductance Plethysmography (RIP) bands and a spirometer. Vital signs, physiologic measurements, and data from RIP and esophageal manometry will be recorded every 30 minutes during the SBT. A study ultrasound to measure diaphragm contractile activity will occur approximately 15 minutes into the SBT.

If the patient successfully passes the SBT, extubation readiness criteria will be confirmed (i.e. cough, gag, handling secretions, no procedures planned). If the patient meets extubation readiness criteria, the recommendation will be for extubation to the clinical team. If the patient does not meet extubation readiness criteria, they return to acute phase management (to whichever group they were randomized), and another SBT will be repeated 24 hours later. If a recommendation for extubation was given but actual extubation is delayed beyond 6 hours, the reasons will be recorded on the case report forms, and the acute phase intervention will be resumed. If the patient is extubated as recommended, the esophageal catheter and RIP bands will remain in place for 1 hour after extubation to monitor post-extubation effort of breathing.

If the patient fails the SBT, they will go on to the weaning phase randomization.

D.3.6 Weaning Phase: The weaning phase is defined as the time from the first SBT until the patient successfully passes an SBT.

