We will measure patient effort of breathing twice daily with esophageal manometry (using Pressure Rate Product [PRP] and Pressure Time Product [PTP]) and once daily using diaphragm ultrasound (using Diaphragm Contractile Activity [DCA]), during the acute and weaning phases in both arms. DCA is obtained by measuring the thickness of the right hemi-diaphragm and calculating the percent difference between diaphragm thickness on inspiration and exhalation. Diaphragm ultrasound measurements will be performed independently by 2 practitioners, one of whom is specifically trained in acute care ultrasound. We will also use ultrasound to measure diaphragm thickness on exhalation and monitor how this changes serially over time as a measure of the architecture of the diaphragm. Finally, we will measure respiratory load (resistance, compliance) daily using spirometry. The clinical team will remain blinded to the results of these measurements in both arms.

D.4.2. Spontaneous Breathing trial respiratory measurements during Airway Occlusion:

Airway Occlusion: Prior to each SBT, we will perform a standardized airway occlusion maneuver to measure neuromuscular capacity with aPiMax (airway) and ePiMax (esophageal), as described in the Preliminary Data. In addition, during airway occlusion we will measure DCA (as above)^{5, 7, 51, 52}, to provide complementary data to PiMax. The clinical team will remain blinded to the results of these measurements in both arms.

D.4.3 Weaning trial measurements during SBTs:

During SBTs, respiratory effort and capacity will be measured with PRP, PTP, inspiratory pressure from esophageal manometry (Pi), Pi/ePiMax, Tension Time Index (TTI), Phase angle (PA), and DCA. Patients will be monitored continuously during the SBT, and all of these measures will be recorded at the beginning of the SBT, and then every 30 minutes (for 5 minute periods) to monitor respiratory muscle endurance over time. The PRP measurements will be shared with the clinical team in both arms because they will be used to help define passage of SBTs (as above). Clinical providers will remain blinded to the results of the other measurements in both arms.

Data Collection timeline	Enrollment	Acute (Daily)	Weaning (Daily)	SBT	Post-Extubation
Demographics (age, race, gender, past medical history, primary diagnoses, comorbidities, PRISM-III-12 severity of illness scores, height, weight, quality of life score)					

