D.4.4 Rationale for respiratory measures: Previous research has highlighted the importance of using multiple assessments of respiratory muscles, as single tests may be misleading.⁶⁷ We will use four classes of respiratory monitoring: esophageal manometry, diaphragm ultrasound, RIP, and ventilator/clinical data. Our primary interest is respiratory muscle strength, which is best characterized during airway occlusion with PiMax. PiMax measurements will be done as soon as the acute phase has resolved, and daily during the weaning phase, because PiMax is not feasible to measure during the acute phase of MV because patients may be too unstable to tolerate airway occlusion. Serial measurements from diaphragm ultrasound can and will be performed daily to assess changes in diaphragm architecture during both acute and weaning phases ^{3, 5-8, 26, 52, 68-73}. Because diaphragm ultrasound is non-invasive, it has advantages although it has not been validated against direct measures of respiratory muscle strength or weaning outcomes. We will attempt such a validation with this study. We anticipate DCA and PRP will provide complementary information regarding patient effort. To isolate diaphragm weakness, a second balloon catheter would be necessary to calculate trans-diaphragm pressure. However, this is not practical for repeated use in children and no double-balloon catheters are commercially available for infants. A second catheter in an already small esophagus may alter the signals further, and impede clinical care if the catheter is left in place. While this leaves open the possibility of intercostal muscles contributing to the weakness, we will complement these data with architectural changes to the diaphragm on ultrasound.

D5 Co-Interventions

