strength we will compare the first measured aPiMax (after resolution of the acute phase, before the first SBT), the trajectory and value of the daily aPiMax during the weaning phase prior to extubation, the lowest and highest measured aPiMax, and aPiMax on the day of extubation against weaning duration. For analysis, aPiMax will be dichotomized at 30 cmH₂O (based on our preliminary data), and weaning duration will be compared between patients with aPiMax > 30 versus ≤ 30 cmH₂O using a t-test with or without log-transformation, or Mann-Whitney U test, depending on the distribution. From our preliminary data, we anticipate at least 35% of patients (n=84) will have aPiMax ≤ 30 cmH₂O. Based on a similar power analysis as presented above, this would allow us to determine whether low aPiMax is associated with a ≥ 1-day increase in weaning duration, with an alpha of 0.05 and power of 0.8. We will perform identical analysis for ePiMax.

Diaphragm Thickness analysis will compound daily ultrasound measures to detect the relative change in diaphragm thickness from study day 1 until passage of an SBT. We will compare the change in thickness after resolution of the acute phase (on the day of the first SBT) against weaning duration, in a similar manner as proposed above for aPiMax. For analysis, diaphragm thickness will be tested as a continuous variable (with Spearman's or Pearson's Correlation), but also categorized into 3 groups (loss of > 10% in thickness, maintenance of thickness (-10% to +10%), and increase in size of > 10%) to account for the potential ill effects of diaphragm hypertrophy (expected in about 10% of patients), using Analysis of Variance (ANOVA) to compare weaning duration between groups. We will characterize how diaphragm thickness changes daily during the weaning phase compared to the thickness on study day 1, as well as the daily thickness compared to that on the day of the first SBT. This will be used to determine whether patients whose trajectory of diaphragm atrophy continues during the weaning phase have a longer weaning duration compared to those who maintain diaphragm thickness or have increased thickness during the weaning phase. We anticipate high correlation between aPiMax and diaphragm atrophy, such that the proportion of patients with > 10% loss in diaphragm thickness will be similar to the proportion of those with aPiMax ≤ 30 cmH₂O, resulting in the same sample size that yield adequate power, as above.

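### Aim 2 tests the lowest and highest aPiMax and ePiMax against weaning duration, although children who wean longer have more readings from which to draw an extreme

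*Combined protocol and SAP*

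**What the plan says.** In the current (276-patient) protocol, section D.6.4.2 and the Aim 2 paragraph of A2 list the aPiMax summaries to be set against weaning duration. They are the value before the first SBT, the daily values and their course, and then "the lowest and highest measured aPiMax, and aPiMax on the day of extubation against weaning duration". aPiMax is split at 30 cmH2O, and durations are compared by t-test (with or without logs) or Mann-Whitney U. For the esophageal measure: "We will perform identical analysis for ePiMax".

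The number of readings depends on how long weaning lasts:
- D.3.4: "Daily SBTs are required and will be performed between 9 and 11 AM".
- D.4.2: "Prior to each SBT, we will perform a standardized airway occlusion maneuver to measure neuromuscular capacity".
- D.4.4: "PiMax measurements will be done as soon as the acute phase has resolved, and daily during the weaning phase".

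The link is not one-to-one. A child who passes but is not ready for extubation stays ventilated, and under D.3.5 "another SBT will be repeated 24 hours later". Weaning can also be suspended for a time.

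The July 2024 SAP, Table 1, lists PiMax on the day of the first SBT and on the day of extubation, both as outcomes compared between arms. It neither mentions nor withdraws the lowest and highest analyses.

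**The concern.** The exposure is built from a set of readings whose size grows with the outcome. A child who passes the first SBT and is extubated has one reading, which is both lowest and highest. A child who weans for five days has several chances to record a low value and several to record a high one. Any day-to-day variation then produces an association with duration that has nothing to do with strength.

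The two errors run in opposite directions. SA2 expects that "the combination of high respiratory load (or effort) with low PiMax will be a major factor leading to prolonged weaning". The lowest-value test leans towards that expectation and the highest-value test leans against it. The trial could report a false confirmation, or two contradictory results from the same readings.

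No other part of the plan repairs this. The hierarchical model in D.6.4.2 has SBT failure as its outcome, not duration. The GEE and mixed models in the July 2024 SAP handle repeated measures; they cannot correct a minimum or maximum already reduced to one number per child.

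**Working it through.** **Inputs from the documents.** 240 children with an SBT; 35% at or below 30 cmH2O, so 0.35 × 240 = 84 against 156; alpha 0.05, power 0.8 for 1 day (all D.6.4.2). SDs of weaning duration 2.1 and 2.8 days, and about 25% passing the first SBT (D.6.4.1). **Not in the documents, so assumed:** between-child SD, day-to-day SD and the daily chance of passing.

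**1. The plan's own figure.** Power = Φ(1/SE − 1.96).
- SD 2.8 in the low group and 2.1 in the other: SE = √(2.8²/84 + 2.1²/156) = 0.349, power 0.82.
- SD 2.8 in both: power 0.75.
- Pooled SD √((2.1² + 2.8²)/2) = 2.475 in both: power 0.85.

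The stated 0.8 is reproduced, so 1 day is a fair yardstick.

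**2. The mechanism.** Take a child with true aPiMax 36 and day-to-day SD 4. One reading is ≤30 with probability Φ(−1.5) = 0.067. For k readings the chance that the lowest is ≤30 is 1 − 0.933^k: 7% for k = 1, 19% for k = 3, 29% for k = 5.

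**3. Null simulation** (1,000 trials of 240 children). A quarter of children have one reading; the rest have 1 + geometric(0.4). Duration is (readings − 1) days + 2 h. aPiMax is a child effect N(36, 12) plus daily noise N(0, s), independent of duration, with no drift. Mann-Whitney on duration, ≤30 against >30:

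| s (cmH2O) | First | Lowest | Highest |
|---|---|---|---|
| 0 | 5.6% | 5.6% | 5.6% |
| 1 | 4.8% | 6.7% | 6.9% |
| 2 | 6.2% | 15.0% | 13.5% |
| 4 | 4.0% | 40.7% | 38.3% |
| 8 | 4.7% | 86.3% | 87.8% |

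From s = 1 to 8 the spurious difference in mean duration (≤30 minus >30) runs from +0.11 to +0.72 day for the lowest and from −0.10 to −0.82 day for the highest. The log t-test gives similar rates (39.5% and 37.2% at s = 4).

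**4. Looser link between readings and duration.** Assume 15% of children have one or two extra readings after passing, and 15% of those still weaning have one to three days without an SBT. The rates at s = 4 are still 32.2% and 32.5%.

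**5. A different model.** Log-normal aPiMax (log-SD 0.5), 35% ≤30 at any single reading, within-child correlation (ICC) varied:
- The model in step 3 has ICC = 144/(144 + s²), so s = 4 corresponds to 0.90.
- At ICC 0.9 the lowest and highest each reject at 32% when mean duration is 1.6 days and at 51% when it is 3.2 days. The 38-41% in step 3 lies between.
- At ICC 0.4 the rates are 98-100%.
- At mean 3.2 days and ICC 0.9 to 0.4, spurious differences are +0.64 to +1.79 days (lowest) and −0.71 to −2.28 days (highest).
- With 30% of later readings missing (ICC 0.8, mean 3.2 days) the rates are 72% and 68%.
- At ICC 1.0 the artefact disappears.
- The share whose lowest value is ≤30 is 45-62% at mean 3.2 days, so n = 84 does not describe that split.

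**6. Drift.** D.6.4.3 anticipates aPiMax improving in some children and falling in others. With +1 or −1 cmH2O/day assigned at random and unrelated to duration, lowest/highest reject at 25%/18% (s = 2) and 46%/41% (s = 4). With common drift at s = 4 they reject at 16%/72% (+1/day) and 77%/19% (−1/day). The first value stays at 4-6%.

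**7. The replacement, under the null.** Logistic regression of SBT pass/fail on that day's aPiMax with an SBT-day term and cluster-robust errors rejects at 4.5-5.9% for s = 1 to 8. With common drift at s = 4 it rejects at 5.1-5.2% with the day term and 7.3-8.1% without. In the model of step 5, a day-stratified, time-updated test rejects at 4-6% for the day's value and 3-6% for the running lowest.

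**The case against.** - **The size is assumed.** The documents give no within-child SD, and C.3.2 argues that PiMax is reliable even under sedation. Most children passed within three days (July 2024 SAP, January 2023 entry), so most have few readings. This stands: at an SD of 1 or less the inflation is slight. The direction does not depend on the assumption.
- **Common drift mixes two problems.** If strength changes steadily with time, any late reading tracks duration; in the same model the last value rejects at 31-35% with +1/day and 41-43% with −1/day (s = 1 to 4). One extreme can also stay near nominal (6.5% for the lowest at +1/day, s = 2). This stands, so the common-drift runs should not be read as the effect of taking an extreme. The no-drift and mixed-drift runs, where the last value stays at 4-6%, isolate that effect.
- **The plan does not say that each summary is split at 30.** True, but the bias does not need the split. In the model of step 5 at mean 3.2 days, the rank correlation of duration with the lowest value is −0.16 to −0.40, and with the highest +0.16 to +0.40, over ICC 0.9 to 0.4.
- **The final SAP may have left these tests behind.** Its Table 1 covers outcomes compared between arms, not Aim 2 predictors. Silence there does not withdraw an analysis the protocol lists.
- **The replacement is only partly planned.** The SBT-day term is new, and the check used a stand-in for the hierarchical model. Both are correct.

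**Conclusion.** The concern holds. As written, the tests of lowest and highest aPiMax and ePiMax against weaning duration do not keep their nominal error rate unless day-to-day variation is close to nil. At assumed day-to-day SDs of 2 to 8 cmH2O with no drift, false-positive rates are about 14% to 88%. The spurious differences approach the 1 day the aim is powered for, and exceed it under some of the assumptions tried. The direction follows from the definitions; the size rests on the assumed variation and weaning times.

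The consequence is limited. The aPiMax before the first SBT, which heads the list of predictors, is sound. The randomised comparisons are untouched, and the point does not reach the trajectory or extubation-day analyses. It should be corrected, but no primary conclusion depends on it.

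**What to change.** 1. Remove the lowest and highest aPiMax and ePiMax from the hypothesis tests against weaning duration, or label them descriptive only. If the tests have already been run, report them as descriptive.
2. Keep aPiMax and ePiMax before the first SBT as the patient-level predictors of duration.
3. Analyse later daily values in the hierarchical SBT pass/fail model of D.6.4.2, adding a term for SBT day. If a lowest value is wanted in a test, enter the running lowest to date as a time-updated covariate stratified by day.
4. Apply the same restriction to the other daily measures in D.6.4.2 only if lowest or highest summaries of them are used; the plan does not name any.
5. Keep the trajectory and extubation-day analyses, with a note that these values are taken during or at the end of the outcome period.
6. State in the SAP which Aim 2 PiMax summaries remain.

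The cost is analysis-plan wording and one added model term. No new data are needed, and the two summaries can still be described.
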